## **Methodology**

**Sample:** The study will be carried out with adolescents in the second and third years of high school in Bizkaia (Spain). The necessary estimated sample size is 500, under a small, anticipated effect size (0.2), a statistical power of 0.8, and a probability level of 0.05. In anticipation of a loss of participants during the follow-ups, the sample size will be increased to 600. Inclusion criteria include adequate reading comprehension and parental and self-informed consent.

**Design and Procedure:** A randomized controlled trial with two groups will be used. Randomization will be done by clusters, using the classroom as the unit. First, the schools will be selected according to their characteristics. Then, for each school and grade, half of the classrooms will be randomly assigned to the experimental condition (values alignment) and the other half to the control condition (traditional educational intervention). Participants will complete an online assessment protocol using Qualtrics, which will be composed of different questionnaires at three time points: (1) pretest (immediately before the intervention), (2) posttest (one week after the intervention), and (3) a three-month follow-up. The study has the approval of the Ethics Committee of the University of Deusto. The trial will be registered on ClinicalTrials.gov.

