**Interventions:** The experimental group will receive the values alignment intervention (Bryan et al., 2016). This includes: (1) reading materials, such as recent journalistic works that expose the deceptive and manipulative marketing practices of food companies and the harmful effects of these practices on society, with particular emphasis on harm to young children and the economically disadvantaged. Stories from other young people will also be included in order to contribute to the perception of widespread outrage and to suggest how that outrage can be channeled into taking a stand against the injustice perpetrated by food companies by eating less unhealthy or healthier food, (2) writing exercises, such as a story with a brief statement of what the participants would tell a younger child about the ads, and (3) an interactive activity, called "Make It Real" in which they are shown pictures of food ads and allowed to write and draw about them, making whatever changes (e.g., crossing out and substituting words) they feel necessary to make the ad "real" (i.e., no longer misleading). The control group will receive a traditional educational intervention on nutrition and physical exercise. This will be of the same duration and will also include reading and writing exercises.

**Measurements:** Healthy and unhealthy food intake will be measured at pretest, posttest, and three-month follow-up using the questionnaire developed by Stok et al. (2015). It consists of

four items that provide an index of unhealthy eating. In addition, according to the content addressed in the intervention sessions in the posttest and three-month follow-up, two attitudinal variables will be evaluated: (1) the alignment of healthy eating habits with the values of adolescents using seven items from Bryan et al. (2019), and (2) the social attractiveness of healthy eating using three items from Bryan et al. (2019), and answered on a five-point scale. Finally, some individual characteristics will be measured through an ad hoc questionnaire: gender, age, socioeconomic status (education and parental profession), height, and weight (to determine BMI).

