**Statistical Analysis:** To evaluate the effect of the intervention on the repeated measures of the dependent variables, a multilevel analysis with MPLUS-8.8 will be used. This will include repeated measures at level one (e.g., healthy and unhealthy food intake), adolescent variables at level two (assigned intervention and potential moderators), and the classroom at level three. It will be determined whether the intervention explains the slope of change of the dependent variables (intervention  $\times$  time interaction). For moderation effects, triple interaction terms will be created using dummy variables or z variables, depending on the nature of the variables. To assess whether the effect of the intervention on healthy and unhealthy food intake is mediated by the attitudinal variables, a structural equation model with a bootstrapping procedure will be estimated ( $N = 10,000$  samples). For the handling of missing values, the full information maximum likelihood method will be used as a general approach, although, depending on the nature of the missing value patterns, other techniques (e.g., multiple imputations or use of auxiliary variables) may be used.

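### The intake effect is tested as a change from pretest with no stated pretest adjustment, which is unbiased but less precise than the data already planned would allow

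*Combined protocol and SAP*

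**What the plan says.** All references are to the Methodology section of the combined protocol and SAP.

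- **Measurements:** "Healthy and unhealthy food intake will be measured at pretest, posttest, and three-month follow-up". The two attitudinal variables are scheduled only at posttest and follow-up, so this point concerns intake alone.
- **Statistical Analysis:** a three-level model has the repeated measures at level one, "adolescent variables at level two (assigned intervention and potential moderators") next, and the classroom at level three. The effect is the intervention by time interaction: "It will be determined whether the intervention explains the slope of change of the dependent variables".
- **Not stated:** whether the intervention also predicts the intercept, whether pretest intake is a covariate, whether the arms share a pretest mean, and how time is coded (visits or weeks, linear or categorical).
- **Design and Procedure:** classrooms are randomised within school and grade, and pretest comes immediately before the intervention.

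**The concern.** When a predictor has an interaction with time, its main effect is normally in the model too. The arms may then differ at pretest, and the interaction becomes a difference in mean change.

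In a randomised comparison measured before treatment, the expected pretest means are equal and an observed gap is chance. The best use of the pretest removes that gap only in proportion to how well pretest predicts follow-up. A change contrast removes all of it and so carries pretest noise into the treatment effect. With about 15 classrooms per arm, chance gaps are to be expected.

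What is at stake is precision on the main outcomes, in a trial sized for a small effect and with a pretest that is collected anyway. If pretest handling is left open, it could also be chosen after the imbalance is known.

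**Working it through.** **1. The plan's own figure.** The plan gives no standard error to reproduce. Its only related figure is the sample size: "The necessary estimated sample size is 500", "under a small, anticipated effect size (0.2), a statistical power of 0.8, and a probability level of 0.05". The two-mean formula gives n per arm = 2(1.96 + 0.84)²/0.2² ≈ 393, or 786 in total two-sided (620 one-sided), not 500. The text does not say whether a pretest correlation was used. That is a separate matter and does not decide this point.

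**2. Inputs.**
- From the plan: "the sample size will be increased to 600"; about 30 classrooms (Budget), hence 600/30 = 20 pupils each and 15 classrooms per arm; visits at pretest, one week and three months.
- Assumed: total variance 1; complete data; the same pupil correlation ρ between any two visits, from 0.4 to 0.8; classroom variance of none, 0.02 stable plus 0.01 classroom-by-time, or 0.05 stable.

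**3. Correlation of classroom means between visits.**

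λ = (stable classroom variance + pupil variance × ρ/20) / (total classroom variance + pupil variance/20)

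At ρ = 0.5:
- no classroom variance: 0.025/0.05 = 0.500
- 0.02 + 0.01: (0.02 + 0.02425)/(0.03 + 0.0485) = 0.564
- 0.05 stable: (0.05 + 0.02375)/(0.05 + 0.0475) = 0.756

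For a contrast at one visit, λ is also the optimal weight for the pretest gap. The change contrast uses weight 1.

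**4. Variance with a common pretest mean, divided by variance with a free pretest difference.**
- One visit (categorical time): (1 + λ)/2.
- Linear slope with times t: [Σt² − (Σt)²/3] / [Σt² − λ(Σt)²/(1 + 2λ)].

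At λ = 0.5:
- one visit: 0.75
- times 0, 1, 2 (Σt² = 5, Σt = 3): 2/2.75 = 0.727
- weeks 0, 1, 13 (Σt² = 170, Σt = 14): 104.67/121 = 0.865

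The excess in the planned standard error is 1/√ratio − 1, which gives 15.5%, 17.3% and 7.5%. Generalised least squares on the classroom means gives the same values.

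**5. Excess standard error of the planned contrast (%).**

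| Contrast | Classroom variance | ρ = 0.4 | 0.5 | 0.7 | 0.8 |
|---|---|---|---|---|---|
| One visit | none | 19.5 | 15.5 | 8.5 | 5.4 |
| | 0.02 + 0.01 | 15.4 | 13.1 | 8.9 | 6.9 |
| | 0.05 stable | 8.2 | 6.7 | 3.9 | 2.5 |
| Slope 0, 1, 2 | none | 22.5 | 17.3 | 9.0 | 5.6 |
| | 0.02 + 0.01 | 17.2 | 14.3 | 9.4 | 7.3 |
| | 0.05 stable | 8.7 | 7.0 | 4.0 | 2.6 |
| Slope in weeks | none | 9.9 | 7.5 | 3.8 | 2.4 |
| | 0.02 + 0.01 | 7.5 | 6.2 | 4.0 | 3.1 |
| | 0.05 stable | 3.7 | 3.0 | 1.7 | 1.1 |

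**6. Power.** A planned contrast with 80% power has a standardised effect of 1.96 + 0.84 = 2.80. If its standard error is k times the better one, power becomes Φ(2.80k − 1.96).
- k = 1.155: 90%
- k = 1.067: 85%
- k = 1.030: 82%
- k = 1.011: 81%

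Only the corner with ρ = 0.4 and no classroom variance goes clearly above this, to 92% (one visit) or 93% (slope 0, 1, 2).

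**The case against.** **The criticised model is inferred.** The plan never says that the arm difference at pretest is free. If the intervention predicted only the slope and time were zero at pretest, the model would already have a common pretest mean. This stands as a limit on certainty. The free reading is the conventional one, and the same sentence in the plan would settle either case.

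**The size is uncertain.** A reader might take a single figure such as 6–15% as the loss. That figure is roughly the one-visit contrast at a correlation of exactly 0.5, whereas the plan's stated target is a slope. With time in weeks and stable classroom variance, the loss may be only 1–3%. This stands, and the size must be given as a range.

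**A reader might infer that the pretest is wasted or the estimate biased.** Neither follows. The interaction uses the pretest, with weight 1. Without clustering, for correlations above 0.5, change is still more precise than ignoring the pretest. Over randomisations the contrast is unbiased, so the loss is one of efficiency.

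**The remedy has its own assumption.** The plan requires parental and pupil consent but does not say whether consent precedes classroom allocation. If it follows, consenting pupils may differ by arm, and imposing equal pretest means would put part of that gap into the effect. This stands and affects the choice of remedy. Allocation within school and grade should also limit chance imbalance, which the calculation ignores.

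**Conclusion.** The point holds as one of efficiency. As written, the plan states no pretest adjustment for intake and, on the ordinary reading, tests a difference in mean change. That is valid but less precise than the alternatives for any correlation below 1.

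Over pupil correlations of 0.4–0.8 and the three classroom variances, the planned standard error is larger than needed by about 2.5–20% (one visit), 2.6–22% (slope 0, 1, 2) or 1–10% (slope in weeks). These figures rest on assumed correlations and variances, an unstated time coding, equal classrooms of 20 and complete data.

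It might be tempting to conclude that 500 was derived for a pretest-adjusted analysis, since that formula gives 504 at a correlation of 0.6 (a change analysis needs 628). The documents do not support this: they state no correlation, and a change analysis would also reach about 500 at a correlation near 0.68.

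**What to change.** For the intake outcomes only, specify one of these as the main analysis before any outcome data are seen:

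1. a multilevel model of posttest and three-month intake, with the pupil's pretest and the classroom-mean pretest as covariates; or
2. a repeated-measures model with one pretest mean common to both arms, and intervention terms only at posttest and three months.

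Keep the plain change model as a sensitivity analysis. State the time coding, and state whether consent and pretest are completed before classroom allocation is known. If consent follows allocation, prefer option 1, because it does not impose equal pretest means. It cannot remove differences in who consents that pretest intake does not capture.

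The cost is a sentence or two in the Statistical Analysis paragraph, with no new data, pupils or visits. Any expected gain should be quoted as a range over assumed correlations.

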## **Project Objectives**

The general objective of this project is to adapt the values alignment intervention to improve obesity-related eating habits in Spanish adolescents. It is therefore a highly innovative project with great potential for social impact in the field of health promotion. The specific objectives

are: (1) to adapt the values alignment intervention to the Spanish culture and context, (2) to evaluate the effects of the intervention in reducing unhealthy food intake and increasing healthy food intake in adolescents, (3) to evaluate differences between adolescents receiving the intervention and those in the control group regarding attitudinal variables related to healthy eating (alignment of healthy eating habits with adolescents' values and social attractiveness of healthy eating), (4) to evaluate potential moderators of the effect of the intervention, specifically socioeconomic status, given that more disadvantaged socioeconomic levels are associated with worse eating habits and greater obesity, gender, given that in the study by Bryan et al. (2019) the effect was more beneficial in boys, and body mass index (BMI), given that those adolescents with a higher BMI may present more consolidated habits of unhealthy food consumption, and (6) to evaluate whether the effect of the intervention on eating behavior is mediated by attitudinal variables.

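### No primary test is named and no multiplicity control is planned; with 0.05 per test assumed, the chance of at least one false positive is about 9 to 10% for the two intake outcomes and up to 18.5% if the two attitude scales also count.

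*Combined protocol and SAP*

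**What the plan says.** **Outcomes.** Under Project Objectives, objective 2 takes two intake outcomes together: "to evaluate the effects of the intervention in reducing unhealthy food intake and increasing healthy food intake in adolescents". Objective 3 adds between-group comparisons on two attitude scales (alignment of healthy eating with adolescents' values, and its social attractiveness). Objective 4 adds three moderators: socioeconomic status, gender and BMI. None of these is called primary or secondary.

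**Sample size.** Methodology, Sample, states: "The necessary estimated sample size is 500". The assumptions are a small effect of 0.2 and "a statistical power of 0.8, and a probability level of 0.05". The sentence does not say which outcome, time point or contrast the 0.2 refers to.

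**Analysis.** Methodology, Statistical Analysis, specifies a three-level model and asks whether the intervention explains the slope of change in the dependent variables, in the plural. On moderation it says: "For moderation effects, triple interaction terms will be created using dummy variables or z variables, depending on the nature of the variables". It does not list the outcomes to which the moderator terms apply. The section gives no significance level, no hierarchy of outcomes and no multiplicity procedure, and it calls nothing exploratory.

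**The concern.** A plan that is followed exactly should settle in advance which result would count as success. Here a significant intervention-by-time effect on any of the outcomes could be presented as evidence that the intervention works, and nothing in the text would contradict that. The chance of a false claim is then higher than the 5% used to size the trial.

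The sample-size statement has the same gap. A power of 0.8 is a property of one specified test, and no such test is identified. A reader cannot tell whether the trial is powered for unhealthy intake, healthy intake, an attitude scale, or a particular follow-up.

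The moderator analyses are a second, larger set of tests. Without an exploratory label or an adjustment, a single significant three-way interaction could be reported as a finding about whom the intervention helps.

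**Working it through.** **Inputs from the documents**
- Level 0.05, power 0.8, effect 0.2, sample size 500 (Methodology, Sample).
- Equal allocation of classrooms within school and grade: "half of the classrooms will be randomly assigned to the experimental condition (values alignment) and the other half to the control condition" (Methodology, Design and Procedure).
- Two intake outcomes, two attitude scales and three moderators (Project Objectives; Methodology, Measurements).
- One intervention-by-time test per dependent variable (Methodology, Statistical Analysis, on the natural reading).

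**Assumptions not in the documents**
- Each test is two-sided at 0.05.
- All null hypotheses are true.
- Correlations between test statistics of 0, 0.3, 0.5 and 0.7 are used as a range.

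**Step 1: can the plan's 500 identify the test?** Reading 0.2 as a standardized mean difference between two equal arms, n per arm = 2(z₁₋α/₂ + z₀.₈)²/0.2².
- Two-sided: 2(1.960 + 0.842)²/0.04, which rounds up to 393 per arm, 786 in total.
- One-sided: 2(1.645 + 0.842)²/0.04, which rounds up to 310 per arm, 620 in total.

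Neither gives 500. A pretest-adjusted comparison comes close with an unstated pretest correlation of about 0.60: 786 × (1 − 0.60²) = 503.04, rounded up to 504. This ignores clustering by classroom. The figure therefore does not reveal which test was meant. Whether 500 is adequate is a separate matter.

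**Step 2: main effects.** For k independent tests, P(at least one false positive) = 1 − 0.95^k.
- k = 2 (both intake outcomes): 1 − 0.9025 = 9.75%.
- k = 4 (adding both attitude scales): 1 − 0.8145 = 18.5%.

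For equicorrelated normal test statistics:

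| Correlation | 2 tests | 4 tests |
|---|---|---|
| 0 | 9.75% | 18.5% |
| 0.3 | 9.5% | 17.4% |
| 0.5 | 9.1% | 15.6% |
| 0.7 | 8.3% | 13.1% |

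The outcome count is itself uncertain. Methodology, Measurements, promises healthy and unhealthy intake but describes only an index of unhealthy eating. With three outcomes the independent figure is 1 − 0.95³ = 14.3%.

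**Step 3: moderation, as a separate family.**
- k = 6 (2 intake outcomes × 3 moderators): 1 − 0.95⁶ = 26.5%.
- k = 12 (4 outcomes × 3 moderators): 1 − 0.95¹² = 46.0%.

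If outcomes are correlated but the moderators act independently, the 12-test figure is 1 − (1 − p₄)³, where p₄ is the four-test rate above. This gives 43.6% at 0.3, 39.8% at 0.5 and 34.4% at 0.7. The 46% is not a ceiling: the Bonferroni bound is 12 × 0.05 = 60%. Testing the two socioeconomic components separately makes 16 tests, and 1 − 0.95¹⁶ = 56.0%.

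**The case against.** The strongest reply is that the plan does imply an order. The general objective is to improve eating habits, and objective 2 is the effect on intake. The attitude scales also serve as proposed mediators, and the moderators are described as potential ones. On that reading, the family that bears on whether the intervention works is the two intake outcomes. Its error rate is about 9 to 10%, just under twice the nominal level. This largely stands as a limit on the size of the problem. It does not remove it, because the order is never stated and objective 3 compares the attitude scales between arms in its own right.

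A reader might infer that every test is run at 0.05 and that the false-positive risk for the trial's main question is therefore 19% or even 46%. The documents do not support that. The level appears only in the sample-size sentence. The 18.5% figure requires the attitude scales to count as equal routes to success, which the plan does not say. A three-way interaction asks for whom the effect differs, so 46% is not an error rate for whether the intervention works. It also requires moderation to be tested on all four outcomes, which is not stated.

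A reader might also infer that separate tests at one week and at three months add further inflation. No such tests are planned. The named test is the slope over the repeated measures, and one test per outcome is a fair reading. What remains open is how time is coded, and what slope is meant for the attitude scales, which Measurements describes only at posttest and follow-up.

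Finally, the plan says the trial will be registered, and the registry may name a primary outcome. That cannot be checked here. If it does, this document should state the same one.

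**Conclusion.** The point holds in a limited form. The plan identifies no primary test, attaches its power to none, and controls multiplicity nowhere. For the behavioural question the consequence is moderate: 9.75% in place of 5% under independence, and about 9% at an assumed correlation of 0.5. If the attitude scales also count as success, it is 18.5% under independence and about 13 to 17% at assumed correlations of 0.7 to 0.3. The moderator family is separate, at 26.5% (6 tests) or 46% (12 tests) under independence.

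All these figures rest on an assumed two-sided 0.05 per test and on all null hypotheses being true. They should be quoted with those conditions. This is worth correcting before the data are analysed, because an after-the-fact choice among outcomes cannot be distinguished from selection on the results.

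**What to change.** In Methodology, Sample and Statistical Analysis:

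1. Name one primary test within the planned multilevel model: the intervention-by-time effect on the unhealthy-eating index, at two-sided 0.05. This is the only intake index that Measurements describes. State how time is coded and which contrast carries the conclusion.
2. Tie the sample-size statement to that test, saying what the 0.2 measures.
3. Make healthy intake and the two attitude scales secondary, with Holm adjustment. For three tests the successive thresholds are 0.05/3 = 0.0167, 0.05/2 = 0.025 and 0.05.
4. State which outcomes the moderator terms apply to. Label all three moderator analyses exploratory, reported as estimates with intervals and no significance claims, or else Holm-adjust them. Holm's first threshold would be 0.05/6 = 0.0083 for 6 tests or 0.05/12 = 0.0042 for 12.

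The planned slope model need not be replaced by a pretest-adjusted three-month comparison. Nor need gender be singled out among the moderators, since Project Objectives gives a reason for each of the three.

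The cost is wording in the protocol and agreement with the registration. The downside is that secondary outcomes, and moderators if adjusted, face a stricter threshold and have less power.

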#### BUDGET

Concept	Amount
Contract for a research assistant with a degree in psychology on a part-time basis (25 hours per week).	20,000
Travel and per diem expenses for researchers [name] and [name] for coordination and adaptation of the intervention materials for Spanish adolescents.	6,100
Incentive vouchers for participants. Vouchers will be raffled among the participants in each classroom to encourage participation. These will have a value of 20 euros and can be exchanged in shopping centers. Two vouchers will be raffled in each of the approximately 30 classrooms.	1,200
Trips to schools.	1,100
Expendable materials, such as markers and paints for intervention activities, which will be given to the adolescents.	1,600
Total	30,000
QUARTERLY WORK PLAN	1 2 3 4
1. Adaptation of the materials for Spanish adolescents	x
2. Acquisition of materials	x
3. Training the research staff on the procedures	x
4. Contacting schools and obtaining permissions	x
5. Application of pretest and intervention measures	x x x
6. One-week and three-month follow-ups	x x
7. Merging and cleaning of databases	x
8. Statistical analysis of data	x x
9. Writing the final report and scientific manuscripts	x
10. Dissemination and transference in conferences, participating schools, and society in general	x

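### The mediation model names no classroom level and no resampling unit; if pupils are resampled, the indirect-effect interval is too narrow under stated conditions, and false positives exceed 5% only when path and ICC are large enough

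*Combined protocol and SAP*

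**What the plan says.** The Design and Procedure paragraph fixes the unit of allocation: "Randomization will be done by clusters, using the classroom as the unit". Allocation is stratified: "for each school and grade, half of the classrooms will be randomly assigned to the experimental condition". The Budget implies the number of units: "Two vouchers will be raffled in each of the approximately 30 classrooms".

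The Statistical Analysis paragraph then describes two separate models. The first estimates the intervention effect on the repeated outcome measures and has three levels, with "adolescent variables at level two (assigned intervention and potential moderators), and the classroom at level three". The second addresses mediation of the effect on intake: "a structural equation model with a bootstrapping procedure will be estimated", using 10,000 samples. For this second model the paragraph does not say whether it is single-level or multilevel, whether pupils or classrooms are resampled, or whether the school-by-grade strata enter. No other section says so.

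Mediation is a stated aim. The last item under Project Objectives is "to evaluate whether the effect of the intervention on eating behavior is mediated by attitudinal variables". Under Measurements, "in the posttest and three-month follow-up, two attitudinal variables will be evaluated", so several indirect effects may be tested.

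**The concern.** An indirect effect is the product of two paths: intervention to attitude, and attitude to intake. Because whole classrooms are allocated, the first path is a contrast between about 30 classrooms, however many pupils they contain. A bootstrap that draws pupils as if independent leaves out the variation between classrooms in the same stratum. Its standard error for the first path is then too small, and so is the interval for the product. Taking 10,000 resamples reduces simulation noise but does not change the unit.

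At stake is a claim that attitudes carry the effect on eating when the intervention has not moved attitudes at all. The plan recognises classroom clustering in one model and does not carry it into the other. It also lists assignment among the pupil-level variables of the first model, so a reader cannot take for granted that the mediation model will treat it as a classroom-level variable.

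**Working it through.** **The plan's own figures.** There is none for mediation. The only computed design figure is the 500 pupils in the Sample paragraph. The two-mean formula with effect size 0.2, power 0.8 and two-sided 0.05 gives 2 x (1.960 + 0.842)^2 / 0.2^2 = 393 per arm, or 786, so 500 is not reproduced without an unstated assumption. Nothing below depends on it.

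**Inputs from the documents.** About 30 classrooms (Budget); 600 pupils planned (Sample: "the sample size will be increased to 600"), hence 600/30 = 20 per classroom; 1:1 allocation of classrooms within school and grade.

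**Inputs assumed.** ICC 0 to 0.10; attitude-to-intake path 0 to 0.4; base layout of 15 strata of two classrooms; either all clustering at classroom level or half of it shared by the stratum.

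**Closed form, for an attitude-to-intake path well away from zero.** Let w be the part of the ICC that lies between classrooms within a stratum. Pupil resampling understates the standard error by a factor of sqrt(1 - ICC + 20w), and the false-positive rate is 2 x Phi(-1.96 / factor).

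| ICC | w | Factor | False positives |
|---|---|---|---|
| 0.05 | 0.05 | sqrt(1.95) = 1.40 | 16.0% |
| 0.10 | 0.10 | sqrt(2.90) = 1.70 | 25.0% |
| 0.05 | 0.025 | sqrt(1.45) = 1.20 | 10.4% |
| 0.10 | 0.05 | sqrt(1.90) = 1.38 | 15.5% |

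The factor falls below 1 only if 20w < ICC, that is, if the between-stratum variance exceeds 19 times w.

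**Main simulation.** 4,000 trials per scenario, 1,000 resamples, percentile intervals, 15 pairs of classrooms of 20, no intervention effect on attitudes, all clustering at classroom level. Simulation error is 0.3 to 0.7 points at rates of 5% to 26%. Pupil-bootstrap false positives:

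| Path | ICC 0 | 0.01 | 0.02 | 0.05 | 0.10 |
|---|---|---|---|---|---|
| 0 | 0.2% | 0.2% | 0.4% | 0.5% | 1.4% |
| 0.05 | 0.9% | 1.3% | 1.2% | 2.7% | 5.5% |
| 0.1 | 2.8% | 3.8% | 6.4% | 8.9% | 16.0% |
| 0.2 | 5.7% | 7.9% | 10.0% | 16.6% | 24.4% |
| 0.4 | 5.8% | 8.5% | 11.2% | 16.4% | 26.1% |

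With half the clustering shared by the stratum, ICC 0.05 and 0.10 give 6.3% and 10.6% (path 0.1), 11.6% and 16.2% (path 0.2), and 11.0% and 15.8% (path 0.4). With four or six classrooms per stratum and path 0.2 to 0.4, ICC 0.05 gives 15.8% to 17.1%, so the layout matters little. A separate, smaller simulation at path 0.3 gave 11.8%, 18.9% and 28.4% at attitude ICC 0.02, 0.05 and 0.10.

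**Coverage when there is an effect.** With a true intervention-to-attitude effect of 0.2 and ICC 0.05, the nominal 95% pupil-bootstrap interval covers 88.4%, 85.2% and 83.9% at path 0.1, 0.2 and 0.4 (91.8%, 90.6% and 88.8% with half shared).

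**Removing each condition.** In the smaller simulation, pupil-bootstrap coverage was 94.4% when attitudes varied only between strata, 94.1% when classrooms differed in intake but not in attitudes, and 96.9% when attitudes were not linked to intake. The narrowing needs both conditions.

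**Remedies, no intervention-to-attitude effect, path 0.2 to 0.4.**
- Two-level interval (Monte Carlo product of the stratum-adjusted classroom contrast and the within-classroom slope): 4.3% to 6.0% with a t reference, 5.8% to 8.4% with a normal one. Residual classroom degrees of freedom are classrooms minus strata minus 1: 30 - 15 - 1 = 14, 30 - 8 - 1 = 21 and 30 - 5 - 1 = 24 in the three layouts tried.
- Classrooms resampled within arm, no stratum terms: about 6% to 9% across separate runs (about 3% to 6% with half shared).
- The same with stratum terms, paired layout: about 2% to 3%, because the resampling breaks the pairs and many strata lose an arm.

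**The case against.** The plan is silent; it does not prescribe a pupil-level bootstrap. The same paragraph opens with a multilevel analysis that names the classroom, so the team knows about clustering and may intend a classroom-aware mediation model. This stands. A reader might infer that the mediation analysis is certain to ignore classrooms, but the documents do not show that. They show a sentence that, followed literally, would leave the randomised unit out, and no text that prevents it.

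A reader might also infer that the two conditions by themselves push false positives above 5%. They do not. When both paths are near zero the interval for a product is conservative, and that offsets the missing classroom variance: the table shows 1.2% to 2.7% at path 0.05 with ICC 0.01 to 0.05, and 3.8% at path 0.1 with ICC 0.01.

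The size rests on assumed values. The simulations use one mediator, one outcome, one time point, equal class sizes and complete data. Adjustment for pretest intake, which the trial measures, could reduce classroom variance and was not varied. Finally, mediation is the last-listed objective, and the main intervention model already has a classroom level. These points limit the weight of the issue but do not supply the missing specification.

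**Conclusion.** The omission is certain: the mediation model has no stated classroom level, cluster adjustment, stratum term or resampling unit in a trial that randomises classrooms. The consequence is conditional. If pupils are resampled in a single-level model, the interval is too narrow when attitudes vary between classrooms within a stratum and are linked to intake. Mediation presupposes the second condition; the documents do not inform the first.

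False positives become material, at about 10% to 26%, for an assumed path of 0.2 to 0.4 and ICC of 0.02 to 0.10 with all clustering at classroom level. With half the clustering shared by the stratum they are about 11% to 16% at ICC 0.05 to 0.10. There is no excess over 5% at path 0, at path 0.05 with ICC up to 0.05, or at path 0.1 with ICC 0.01. Confidence is high for the omission and the direction, and lower for the size. This should be fixed before analysis. It does not touch the model for the intervention effect on intake.

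**What to change.** Replace the mediation sentence in the Statistical Analysis paragraph with a two-level mediation model that states:

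- assignment enters at classroom level;
- the school-by-grade strata used in the randomisation are covariates;
- the attitude-to-intake path is the within-classroom path;
- the indirect-effect interval (a Monte Carlo product, for example) uses a small-sample t reference for the intervention-to-attitude path, with residual classroom degrees of freedom from the actual layout.

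If a bootstrap is kept, resample whole classrooms, not pupils, and acknowledge its limits with about 30 classrooms. Resampling within arm should not be combined with stratum terms, which is conservative in the paired layout; without them it is somewhat liberal when all clustering is at classroom level.

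The cost is one or two sentences, a little programming and no new data. At an assumed ICC of 0.05 and path 0.2 to 0.4, the two-level interval is about 1.4 to 1.5 times the pupil-bootstrap width (about 1.25 to 1.3 times with half the clustering shared), so the mediation test has less power. Part of the apparent power under pupil resampling comes from an interval that is too narrow.
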